7.2 Significant Interaction Analysis Plan

A significant interaction suggests that the EAA mixture or placebo effect is dependent upon the time effect. This implies the EAA mixture or placebo effect will have to be assessed separately within each time point, and vice versa. Since the two EAA mixture and placebo groups are independent, an analysis of covariance (ANCOVA) model will be used to assess the EAA mixture or placebo effect for each time point (midpoint & final). A repeated measures analysis of variance (ANOVA) model will be used to assess the time effect for EAA mixture or placebo, where the repeated measure is time. A Bonferroni-corrected α -level of 2.5% will be used to determine the statistical significance of these tests.

7.3 Sample Size Calculation & Power Analysis

A total of 60 completed subjects will be required for this study with 30 subjects per EAA mixture and placebo group. The following power calculations are based on the analysis of the results of the six minute walk, leg strength, grip strength and 10 meter gait speed from our pilot studies. Insulin sensitivity and plasma lipids will be secondary end points. These calculations assume the “worst case” scenario where a significant EAA mixture or placebo-by-time interaction is detected and the covariates are not significant. In this case, the EAA mixture or placebo effect would be assessed separately within each time point, and the time effect would be assessed for each group.

7.4 EAA mixture or placebo Effect

The following power calculations are based on a two-sample t-test which is being used as an approximation of the ANCOVA model. With 30 subjects in each EAA mixture and placebo group and an α -level of 2.5%, a two-sample t-test will have approximately 80% power to detect effect sizes of 0.82 standard deviation units or larger. **Table 4** presents the hypothesized group means for each endpoint as well as the corresponding EAA mixture or placebo effect and power estimate. These estimates correspond to approximately 25% (6-minute walk) to 50% (gait speed) of the differences in the values between individuals with heart failure vs age-matched healthy controls as determined in our Phase I protocol. Our previous outcome studies with EAAs indicate that these levels of improvement are expected (e.g., 11, 12, 13).

Table 4. Hypothesized group means and within group standard deviation used to estimate the power of the nutritional therapy effect when N=60 (30 per group) are enrolled. The calculations assume that an α -level of 2.5% will be used to determine statistical significance.

Endpoint	Hypothesized Mean Changes [#]		σ_{Δ} ^{\$}	Effect Size	Power (%)
	Control	Nutritional product			
6 Minute Walk ^a	0	105.1	89.3	1.18	98.67
Leg Strength ^a	0	11.0	13.3	0.83	81.31
Grip Strength ^a	0	4.1	4.6	0.89	87.19
10m Gait Speed ^a	0	0.23	0.28	0.82	80.80

#Means of the baseline and post-treatment changes for each group.

§Estimated within group standard deviation of the changes.

^aEstimates of σ_{Δ} were obtained from pilot studies performed at the UAMS Pepper Center.

7.5 Time Effect

The following power calculations are based on a paired t-test which is being used as an approximation of the repeated measures ANOVA model. With 60 subjects within each time point, a paired t-test using a 2.5% α -level will have 80% power to detect effect sizes of 0.41 standard deviations or larger. Note that the variance of the difference (σ_{Δ}^2) in the measures can be calculated using the following formula: $\sigma_{\Delta}^2 = \sigma_M^2 + \sigma_F^2 - 2\rho\sigma_M\sigma_F$, where ρ is the correlation between the mid-point (8 weeks) and final (16 weeks) measures, and σ_M and σ_F represent the standard deviations for the mid-point and final assessments, respectively.

Assuming the standard deviations for the mid-point and final measures are similar, the equation can be

simplified to $\sigma_{\Delta}^2 = 2\sigma_{\Delta}^2(1 - \rho)$. Using the simplified formula and our estimates of the standard deviations from Table 4,

Table 5 presents the detectable differences that correspond to an effect size of 0.41.

Table 5. Detectable differences associated with an effect size of 0.41.

Endpoint	ρ	σ_{Δ}	Detectable Difference
6 Minute Walk	0.25	109.4	44.9
	0.50	89.3	36.6
	0.75	63.1	25.9
Leg Strength	0.25	16.3	6.7
	0.50	13.3	5.5
	0.75	9.4	3.9
Grip Strength	0.25	5.6	2.3
	0.50	4.6	1.9
	0.75	3.3	1.4
Gait Speed	0.25	0.34	0.14
	0.50	0.28	0.12
	0.75	0.20	0.08

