3.0 Study Design and Procedures

This is a randomized, double blind, prospective study examining the effects of 12 weeks' ingestion of either EAA mixture or placebo on physical function. We will also examine several blood parameters and fecal microbiome in both groups of subjects (see section 5.1). Up to 80 subjects ages 60 to 89 will be enrolled to obtain 60 completers (30 per group).

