7.0 Data Analysis

7.1 Statistical Analysis plan

A repeated measures analysis of covariance (ANCOVA) model will be used to evaluate the effects of EAA mixture and placebo on each parameter. The model will contain EAA mixture versus placebo and time main effects as well as their interaction. Baseline measures will be included in the model as a covariate to control for each subject's starting point. The model will also include factors to account for lean body mass and gender. A non-significant interaction would imply that the EAA mixture or placebo and time effects are not dependent upon one another and that main effects can be tested. The significance of the interaction and main effects will be determined using a 5% α -level. Covariates that may need to be accounted for such as age and lean body mass may be added to the model as a separate exploratory analysis.

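### Section 7.5 powers the within-group time test on 60 subjects, but each group has 30: power at 0.41 SD is about 46%, not 80%, and 80% power needs about 0.59 SD

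*Combined protocol and SAP*

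**What the plan says.** Section 7.3 fixes the numbers: "A total of 60 completed subjects will be required for this study with 30 subjects per EAA mixture and placebo group". It adds that the power calculations take a worst case in which the treatment-by-time interaction is significant. The treatment effect is then tested at each time point, and "the time effect would be assessed for each group".

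Section 7.2 describes the same follow-up. A repeated measures ANOVA "will be used to assess the time effect for EAA mixture or placebo, where the repeated measure is time", and a Bonferroni-corrected level of "2.5% will be used to determine the statistical significance of these tests".

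Section 7.1 covers the other branch. A non-significant interaction is taken to mean that the treatment and "time effects are not dependent upon one another and that main effects can be tested"; the level for main effects there is 5%.

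Section 7.4 powers the between-group comparison with 30 per group at 2.5%. Section 7.5 then powers the time effect: "With 60 subjects within each time point, a paired t-test using a 2.5"% level "will have 80% power to detect effect sizes of 0.41 standard deviations or larger". Table 5 multiplies 0.41 by an SD for each endpoint at correlations of 0.25, 0.50 and 0.75.

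**The concern.** The level in Section 7.5 (2.5%) and the scenario set in Section 7.3 both belong to the significant-interaction branch, where time is tested inside one group. That test has 30 pairs. The sample size in Section 7.5 (60) is the whole trial. The two do not belong to the same test.

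If the power statement is taken at face value, a non-significant mid-point-to-final change within a group could be read as fair evidence against a change of 0.41 SD. With 30 pairs the test would miss such a change more often than it finds it. Table 5 would also understate the smallest change that each group can show with 80% power.

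**Working it through.** **Inputs.** Completers: 60 in total, 30 per group (Sections 3.0 and 7.3). Level: 2.5% (Sections 7.2 and 7.5). Effect size: 0.41 SD of the paired difference (Section 7.5). SDs: 89.3, 13.3, 4.6 and 0.28 (Table 4). The plan does not state sidedness; I assume two-sided and test that in step 2.

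**Formula.** For a paired t-test with n pairs and standardised effect d, the statistic follows a noncentral t distribution with n − 1 df and noncentrality d√n. Two-sided power at level α is the probability that |t| exceeds the 1 − α/2 point of the central t distribution.

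**Step 1: the plan's own figure.** With n = 60, noncentrality is 0.41 × √60 = 3.176 and the critical value (59 df, 0.9875 point) is 2.300. Power is 80.7%. With n = 59 it is 79.9%, so 60 is the smallest number of pairs that supports the claim.

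**Step 2: sidedness.** I recomputed Table 4 as a two-sample t-test with 30 per group at 2.5%:

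| Endpoint | Printed power (%) | Two-sided (%) | One-sided (%) |
|---|---|---|---|
| 6-minute walk | 98.67 | 98.7 | 99.4 |
| Leg strength | 81.31 | 81.4 | 88.3 |
| Grip strength | 87.19 | 87.2 | 92.4 |
| Gait speed | 80.80 | 80.8 | 87.9 |

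Two-sided testing matches both Section 7.5 and Table 4. One-sided testing does not match Table 4.

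**Step 3: the test that the plan describes.** With n = 30, noncentrality is 0.41 × √30 = 2.246 and the critical value (29 df) is 2.364. Power is 46.3%. Solving for 80% power gives d = 0.589, and 0.589 / 0.41 = 1.44.

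**Step 4: other readings.**

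| Reading | Power at 0.41 SD | Effect for 80% power |
|---|---|---|
| n = 30, two-sided 2.5% | 46.3% | 0.589 SD |
| n = 30, error pooled over both groups (58 df), two-sided 2.5% | 48.2% | 0.575 SD |
| n = 30, one-sided 2.5% | 58.4% | 0.529 SD |
| n = 60, pooled main effect, two-sided 5% | 87.8% | 0.368 SD |

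None of the readings with 30 pairs reaches 80%. The pooled reading exceeds it, but at a level that Section 7.5 does not use and in a branch that Section 7.3 does not assume.

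**Step 5: Table 5.** Corrected difference = 0.5887 × Table 4 SD × √(2(1 − ρ)). For the 6-minute walk at ρ = 0.50 this is 0.5887 × 89.3 × 1 = 52.6. Printed values are in brackets.

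| Endpoint | ρ = 0.25 | ρ = 0.50 | ρ = 0.75 |
|---|---|---|---|
| 6-minute walk | 64.4 (44.9) | 52.6 (36.6) | 37.2 (25.9) |
| Leg strength | 9.6 (6.7) | 7.8 (5.5) | 5.5 (3.9) |
| Grip strength | 3.3 (2.3) | 2.7 (1.9) | 1.9 (1.4) |
| Gait speed | 0.20 (0.14) | 0.16 (0.12) | 0.12 (0.08) |

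At the printed differences and printed SDs, power with 30 pairs runs from 44.2% (gait speed, ρ = 0.75) to 50.2% (gait speed, ρ = 0.50). The spread is rounding in the table.

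**Side check on the SD.** Table 4 labels its SDs as SDs of changes, while Section 7.5 describes SDs of the mid-point and final assessments. This is ambiguous but not shown to be an error. With B, M and F for baseline, mid-point and final, F − M = (F − B) − (M − B). So var(F − M) = 2σ²(1 − ρ) holds whether σ and ρ both refer to single-time values or both to changes from baseline, given similar SDs.

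**The case against.** The best reply is that Section 7.5 never says the test is within a group. Sixty subjects at each time point is literally true of the whole trial. If a pooled test was meant, the sample size is right and the level is the slip: at 5%, power at 0.41 SD is 87.8% and the stated 80% is conservative. The documents show that 60 and 2.5% do not go together; they do not say outright which is wrong. That much stands, but the within-group reading is clearly the better one. Section 7.3 says that the calculations assume a significant interaction, and 2.5% is the level for that branch. The pooled reading would also leave Section 7.5 in need of correction.

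A second point is that the factor of 1.44 does not hold exactly against each printed row of Table 5. The ratio of the unrounded corrected value to the printed value runs from 1.37 (grip strength at ρ = 0.75 and gait speed at ρ = 0.50) to 1.46 (gait speed at ρ = 0.75). This is true, and it comes from rounding in the printed table.

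A third point is that little depends on this. Both hypotheses in Section 2.0 are comparisons with placebo, and a within-group change can establish neither. This also stands, and it is why the point is minor. The SD labels and the week numbers do not bear on the sample-size error; they are noted only because the same section has to be rewritten.

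**Conclusion.** The power statement in Section 7.5 is wrong for the test that the plan describes. For the within-group time test with 30 completers, power at 0.41 SD is about 46%, and the smallest effect detected with 80% power is about 0.59 SD, 44% larger than stated. Table 5 needs the same correction.

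This rests on the branch stated in Section 7.3 and on two-sided testing, which is inferred because it reproduces the plan's own figures. Across the readings with 30 pairs, power is 46% to 58% and the 80%-power effect is 0.53 to 0.59 SD.

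The severity is minor and confidence is high. The correction to n does not touch the between-group power in Section 7.4 or the target of 60 completers.

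**What to change.** - In Section 7.5, replace 60 subjects with 30 subjects per group and 0.41 with 0.59, and state that the test is two-sided if that is meant.
- Rebuild Table 5 with the corrected differences.
- If a pooled test on 60 subjects is also wanted, present it only for the non-significant-interaction branch, at 5%, with 80% power at about 0.37 SD.
- Keep the 2(1 − ρ) factor and say whether σ and ρ refer to single-time values or to changes from baseline. If the authors confirm single-time SDs, check the Table 4 label and powers.
- Reconcile the mid-point and final times of 8 and 16 weeks in Section 7.5 with the testing at weeks 6 and 12 in Section 1.0.
- Add a sentence that the correction to n leaves Section 7.4 and the 60-completer target unchanged.

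The cost is a change of wording and one rebuilt table, with less favourable detectable effects within groups. No extra patients are needed. Keeping 80% power at 0.41 SD in each group would take 60 pairs per group, or 120 completers; that is not proposed for a conditional follow-up test.

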Treatment of the underlying cause of heart failure would be optimal. Indeed, pharmacological treatment of heart failure predominantly targets the improvement of cardiac performance.

Heart failure may be treated with varying degrees of success with a variety of drugs, including angiotensin-converting (ACE-inhibitors, angiotensin II, beta blockers, diuretics, digoxin, nitrates and others). However, treating systolic heart failure pharmacologically may be quite complex in the elderly. More than 50% of individuals over age 65 with heart failure have at least four co-morbidities (8), and these may complicate therapy of heart failure. Adverse responses to pharmacological therapy are not uncommon, including the fact that both ACE inhibitors and beta blockers can adversely affect muscle function (9). Further, HFPEF is becoming more widely recognized, and to date, despite the expenditure of millions of dollars and years of time and effort, not one large-scale clinical study of a single drug therapy has demonstrated a substantial beneficial outcome. This disappointing reality may reflect the difficulty of treating a syndrome with diverse causes, interacting complex pathogenesis, and multiple co-morbidities with an entirely drug-oriented approach. Reduced exercise capacity is a prominent clinical feature of heart failure. This leads to progressive muscle weakness and a vicious cycle of sedentary behavior, weight gain, and subsequent development of metabolic abnormalities and sarcopenia.

In this study we will perform a randomized clinical trial of a commercially produced nutritional supplement (EAA mixture Essential Blends, Fairbanks, AK) as compared to a placebo in order to determine effects on physical function and health-related quality of life. Subjects will ingest either the EAA mixture product or placebo every day for 12 consecutive weeks. Outcomes will be determined by comparing the results of physical and functional tests from weeks -1 to 6 and 12.

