2.0 Hypotheses

1. We propose that 12 weeks of regular consumption of EAA mixture will improve physical function in individuals with heart failure as compared to placebo.
2. We propose that regular consumption of EAA mixture will improve health-related quality of life as compared to placebo.

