If not performed at visit 1, the physical exam will be performed at this visit. Randomization will be performed as mentioned below. The following assessments will be performed: functional (6-minute walk distance), SF-36 health questionnaire, a whole-body DEXA scan for lean mass measurement, strength (Cybex testing of maximal voluntary contraction of each leg; bilateral hand grip strength). Subjects will be provided with forms and training for recording their dietary intake over a 3-day period during the next week. Study staff will dispense approximately 10 days' worth of study product and a consumption diary for subjects to complete after ingesting each dose. Future visits will be scheduled.

Visits 3-7: Subjects will come to the IOA weekly to return their urine samples, empty supplement containers and consumption diary. They will be asked about any adverse events since last visit. Study staff will dispense more study product and a consumption diary.

Visit 8: Subjects will be asked about any adverse events since last visit. They will return their empty supplement containers and consumption diary. In no particular order, the following assessments will be performed: strength (Cybex testing of maximal voluntary contraction of

each leg; bilateral hand grip strength), functional (6-minute walk distance), SF-36 health questionnaire. Study staff will dispense more study product, a consumption diary, and another 3-day diet diary.

Visits 9-12: Subjects will come to the IOA weekly to return their empty supplement containers and consumption diary. They will be asked about any adverse events since last visit. Study staff will dispense more study product and a consumption diary.

Visit 13: Subjects will come to the IOA to return their empty supplement containers and consumption diary. They will be asked about any adverse events since last visit. Study staff will dispense more study product and a consumption diary. Subjects will be provided with a drink containing 30mg of a stable isotope of creatine (D-3, Cambridge Isotopes Laboratory, Tewksbury, MA). They will be asked to collect 3 separate urine samples over the next 48 hours at approximately 24-hour intervals and return them to UAMS at their next visit. Subjects will be issued a stool sample collection kit to use just prior to visit 14 and another 3-day diet diary.

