Visit 14: Subjects must come to this visit having fasted overnight. They will be asked about any adverse events since last visit. They will return their diet records, empty supplement containers, any full supplement containers, their stool sample, and their consumption diary. Study staff will administer and score the SLUMS test for dementia. A fasting blood sample (~30 mL) will be drawn. After the blood sample is drawn, subjects will be offered a meal and beverages. A urine sample will be collected for dipstick proteinuria.

The following assessments will be performed: functional (6-minute walk distance), SF-36 health questionnaire, a whole-body DEXA scan for lean mass measurement, strength (Cybex testing of maximal voluntary contraction of each leg; bilateral hand grip strength). At the end of this visit, subject will have no further study visits.

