3.4 Randomization

We will use computer randomization to assign subjects to one of two possible treatment groups. The randomization procedure will be stratified by gender. A randomization procedure will be implemented using an Excel spreadsheet. As a participant is identified and enrolled on study, the study coordinator will ascertain gender, which will determine the next randomization.

A: subjects will consume 9g of EAA mixture supplement twice daily for 12 consecutive weeks.

B: subjects will consume 9g of placebo twice daily for 12 consecutive weeks.

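### Section 7.5 powers the within-group time effect on mid-point-to-final change, at weeks 8 and 16 that this 12-week trial does not have, and Table 5 needs recomputing from baseline with 30 per group

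*Combined protocol and SAP*

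**What the plan says.** **Timing.** Section 7.5 defines ρ as "the correlation between the mid-point (8 weeks) and final (16 weeks) measures". Section 3.4 has 12 weeks of product: "subjects will consume 9g of EAA mixture supplement twice daily for 12 consecutive weeks". Strength, walk and SF-36 are assessed at Visits 2, 8 and 14 (Table of Events and Section 3.1). Visits are weekly ("Visits 3-7: Subjects will come to the IOA weekly", and likewise for Visits 9-12), and of Visit 14 Section 3.1 says: "At the end of this visit, subject will have no further study visits".

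**Contrast.** The variance formula in Section 7.5 has two SDs, which "represent the standard deviations for the mid-point and final assessments, respectively". It has no baseline term. Section 1.0 says: "Outcomes will be determined by comparing the results of physical and functional tests from weeks -1 to 6 and 12". The footnote to Table 4 describes its entries as "Means of the baseline and post-treatment changes for each group".

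**Model.** Section 7.1 enters baseline as a covariate. Section 7.2 names midpoint and final as the time points for the between-group ANCOVA. It gives the within-group time effect to a repeated measures ANOVA but does not list that model's time levels.

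**Numbers.** Section 7.3 assumes a significant interaction, with time then assessed in each group. Section 7.5 uses 60 subjects and a 2.5% level, and states 80% power at 0.41 SD. Table 5 converts 0.41 SD to detectable differences at three values of ρ.

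**The concern.** The wrong weeks change no printed figure, because week does not enter the formula. They do show that Section 7.5 was not matched to this trial's schedule, and they leave the analyst without a usable definition of the two measures.

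The contrast matters more. A mid-point-to-final difference cannot see anything that happened between baseline and week 6. An arm that improved early and held its gain would show no time effect. An arm that improved steadily would be credited with half its gain. The within-group result could then contradict Section 1.0, which measures change from week -1.

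Table 5 has two further faults. It feeds an SD of baseline-to-post change into a formula that expects the SD of a single measurement. It also uses the whole sample for a test that Section 7.3 places within each group.

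**Working it through.** **1. Schedule.** With Visit 2 as baseline and weekly visits, Visits 3-7 are weeks 1-5, Visit 8 is week 6, Visits 9-13 are weeks 7-11 and Visit 14 is week 12. Week 16 would fall 16 − 12 = 4 weeks after the last product and the last visit. Week 8 falls at Visit 10, which has no function tests.

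**2. The plan's own figure.** Paired t-test, noncentral t, n = 60, two-sided α = 0.025, noncentrality 0.41 × √60 = 3.18. Power is 80.7%, and the effect size for exactly 80% is 0.407. The stated 0.41 SD therefore reproduces. (One-sided 2.5% would give 87.8%, so two-sided is the variant used.)

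**3. Table 5.** It reproduces, to within one in the last printed digit, as 0.41 × SD × √(2(1 − ρ)), with Table 4's SD of change put in as SD. For the walk (SD 89.3):

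| ρ | SD of difference | × 0.41 | Table 5 |
|---|---|---|---|
| 0.25 | 89.3 × √1.5 = 109.4 | 44.9 | 44.9 |
| 0.50 | 89.3 × √1.0 = 89.3 | 36.6 | 36.6 |
| 0.75 | 89.3 × √0.5 = 63.1 | 25.9 | 25.9 |

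The SD in 2σ²(1 − ρ) should be that of one measurement. Table 4's 89.3 is already the SD of a difference. The two coincide only when 2(1 − ρ) = 1, that is at ρ = 0.50. The printed simplified formula has the same symbol on both sides, which hides the substitution.

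**4. What a mid-to-final test would miss.** Inputs: Table 4's walk gain of 105.1 in the active arm, the SDs in step 3, n = 30 per group (Section 7.3), two-sided 2.5%. The share of the gain reached by week 6 is my assumption, since the documents give no trajectory.

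| Share by week 6 | Gain left, week 6 to 12 | Power at ρ = 0.25 / 0.50 / 0.75 |
|---|---|---|
| 0% | 105.1 | 99.7 / 100 / 100% |
| 50% | 105.1 × 0.50 = 52.6 | 60.9 / 80.0 / 98.3% |
| 75% | 105.1 × 0.25 = 26.3 | 16.3 / 24.2 / 47.6% |
| 100% | 0 | 2.5% (α only) |

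A baseline-to-final paired test of the same gain has effect size 105.1 / 89.3 = 1.18 and power of about 100% in every row.

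**5. Table 5 recomputed from baseline, per group.** For baseline to week 12, Table 4's SD applies directly, with no ρ factor. At n = 30 the noncentrality at 0.41 SD is 0.41 × √30 = 2.25, and power is 46.3%. For 80% power the effect size must be 0.589 SD.

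| Endpoint | SD of change | 0.41 SD (n = 60) | 0.589 SD (n = 30) | Table 4 gain |
|---|---|---|---|---|
| 6-minute walk | 89.3 | 36.6 | 52.6 | 105.1 |
| Leg strength | 13.3 | 5.5 | 7.8 | 11.0 |
| Grip strength | 4.6 | 1.9 | 2.7 | 4.1 |
| Gait speed | 0.28 | 0.115 | 0.165 | 0.23 |

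The walk figure of 52.6 matches half of 105.1 in step 4 by coincidence. Every recomputed value is still below the gain hypothesised in Table 4.

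**The case against.** **Section 7.5 is a power approximation, not the definition of the test.** This is fair. The test is set in Section 7.2, which does not list the levels of the within-group ANOVA. Section 1.0, and the use of plain ANOVA for time where the group effect gets ANCOVA, are both compatible with baseline being a level. So a reader might infer that the analysis is certain to overlook early improvement, and the documents do not establish that. A two-level reading is the more natural one, because Section 7.1 makes baseline a covariate, Section 7.2 names only midpoint and final, and Section 7.5 uses only those two. On the other reading, the power statement belongs to a different contrast. Either way the text needs correcting.

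**The main efficacy test is untouched.** This stands in full. A reader might infer that the trial cannot see an early benefit over placebo. It can. Hypothesis 1 is that "12 weeks of regular consumption of EAA mixture will improve physical function in individuals with heart failure as compared to placebo", which is a between-group claim. It is tested by the baseline-adjusted models of Sections 7.1 and 7.2 and powered separately in Section 7.4. A gain complete by week 6 and held would appear as a group difference at both visits. For the same reason, a within-arm change from baseline is not a test of Hypothesis 1, since it has no placebo comparison.

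**A post-baseline time factor is a legitimate model.** It is, where baseline is a covariate. It answers a different question from the change since week -1 that Section 1.0 describes.

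**Sixty subjects could be meant for a pooled time effect.** Section 7.3 rules this out for these calculations. It assumes an interaction and time tested in each group, and the 2.5% level in Section 7.5 is the one that Section 7.2 sets for that case.

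**Conclusion.** The point holds for the secondary, within-group time effect. The 8- and 16-week labels are wrong on the documents' own schedule. The powered contrast omits baseline, so it either misses gain made by week 6 or does not match the analysis, depending on what Section 7.2 intends. Table 5 misuses Table 4's SDs except at ρ = 0.50. At the per-group size of 30, power at 0.41 SD is about 46% rather than 80%, and the effect detectable with 80% power rises from 0.41 to about 0.59 SD.

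The per-group power figures rest on a two-sided 2.5% level and 30 completers per group. The detectable differences also rest on Table 4's SDs. The loss of power under an early gain rests, in addition, on assumed trajectories and is illustrative. Nothing here weakens the comparison with placebo.

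**What to change.** - **Section 7.5:** replace the 8- and 16-week labels with week 6 (Visit 8) and week 12 (Visit 14).
- **Section 7.2:** state that the within-group repeated measures ANOVA has levels baseline, week 6 and week 12, with contrasts baseline to week 6 and baseline to week 12. Keep baseline as a covariate only in the Section 7.1 model and the between-group ANCOVA, so that it is not both covariate and outcome in one model.
- **Table 5:** recompute it; relabelling is not enough. For baseline to week 12, use Table 4's SDs of change directly and drop the ρ rows. If the same SDs are used for baseline to week 6, say that this is an assumption. Use n = 30 and give the detectable differences as 52.6 (walk), 7.8 (leg strength), 2.7 (grip strength) and 0.165 (gait speed). State that power at 0.41 SD is about 46%.

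The cost is SAP wording and one recalculated table. All three assessments are already scheduled. The downside is that the stated detectable differences become less favourable. The change should be made before the blind is broken, so that the contrast is not chosen after the results are seen.

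### Section 7.5 puts Table 4's standard deviations of change into a formula defined for single-visit standard deviations, so as the terms are defined Tables 4 and 5 agree only at a correlation of 0.50.

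*Combined protocol and SAP*

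**What the plan says.** Section 7.4, Table 4, gives an SD for each endpoint under the symbol σ_Δ. Its footnote defines the column as "Estimated within group standard deviation of the changes", and the companion footnote describes the means as "Means of the baseline and post-treatment changes for each group". The six-minute walk row reads "105.1 89.3 1.18 98.67" and the leg strength row "11.0 13.3 0.83 81.31": mean change, SD, effect size, power. A further note attributes the SDs to pilot studies.

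Section 7.5 covers the time effect: "With 60 subjects within each time point, a paired t-test using a 2.5"% level is said to have "80% power to detect effect sizes of 0.41 standard deviations or larger". The section writes the variance of the difference as σ_M² + σ_F² − 2ρσ_Mσ_F, with σ_M and σ_F the SDs at the mid-point and final assessments and ρ the correlation between those two measures. Taking the two SDs as similar, it prints the simplification σ_Δ² = 2σ_Δ²(1 − ρ), then builds Table 5 "Using the simplified formula and our estimates of the standard deviations from Table 4", for ρ = 0.25, 0.50 and 0.75.

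Section 7.2 supplies the 2.5% level: the Bonferroni-corrected value "will be used to determine the statistical significance of these tests".

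**The concern.** The Section 7.5 formula takes the SD of a measurement at one visit and returns the SD of a difference between two visits. An SD of change from baseline is already the SD of a difference. Entering it where a single-visit SD belongs applies a correlation adjustment to a quantity that already reflects a correlation. The printed identity shows the problem: with the same symbol on both sides it can be true only if 2(1 − ρ) = 1, that is, ρ = 0.50.

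Two things are at stake. Most of the detectable differences in Table 5 may not have the power claimed for them. And the same ambiguity reaches Table 4, which holds the only hypothesized effects and powers offered in support of 30 completers per group.

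**Working it through.** **Inputs.** Table 4 mean changes: 105.1, 11.0, 4.1, 0.23. Table 4 SDs: 89.3, 13.3, 4.6, 0.28 (walk, leg, grip, gait). Section 7.4: 30 per group, two-sample t-test, 2.5%. Section 7.5: n = 60, paired t-test, 2.5%, effect size 0.41. Powers below use the noncentral t distribution. The plan does not state sidedness. Two-sided is inferred because it fits: with n = 60 and two-sided 2.5%, the effect size for 80% power is 0.407 (80.7% power at 0.41), whereas one-sided 2.5% would give 0.368.

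**Step 1: reproduce Table 4, using its SDs as SDs of change.** Effect size = mean change / SD; for example 105.1/89.3 = 1.18. Powers come out at 98.67, 81.38, 87.19 and 80.80%, against the printed 98.67, 81.31, 87.19 and 80.80%.

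**Step 2: reproduce Table 5, using the same SDs as single-visit SDs.** SD of difference = Table 4 SD × √(2(1 − ρ)). The multiplier is √1.5 = 1.225 at ρ = 0.25, 1 at 0.50 and √0.5 = 0.707 at 0.75. The detectable difference is 0.41 times the result.

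| Endpoint | SD at ρ = 0.25 / 0.50 / 0.75 | × 0.41 | Printed detectable difference |
|---|---|---|---|
| Walk | 109.37 / 89.30 / 63.14 | 44.8 / 36.6 / 25.9 | 44.9 / 36.6 / 25.9 |
| Leg | 16.29 / 13.30 / 9.40 | 6.68 / 5.45 / 3.86 | 6.7 / 5.5 / 3.9 |
| Grip | 5.63 / 4.60 / 3.25 | 2.31 / 1.89 / 1.33 | 2.3 / 1.9 / 1.4 |
| Gait | 0.343 / 0.280 / 0.198 | 0.141 / 0.115 / 0.081 | 0.14 / 0.12 / 0.08 |

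All twelve rows match within rounding. The small gaps arise because the plan multiplied rounded SDs: 0.41 × 109.4 = 44.85 and 0.41 × 3.3 = 1.35. Every ρ = 0.50 row repeats the Table 4 SD. So the substitution is visible in the numbers, whether or not the doubled symbol is a typing slip.

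**Step 3: if the Table 4 SDs are SDs of change.** Assume also that they apply to the mid-to-final change, which the documents do not say. The detectable difference is then 0.41 × Table 4 SD for every ρ: 36.6, 5.5, 1.9 and 0.115. Power at the printed differences, n = 60, two-sided 2.5%:

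| Endpoint | ρ = 0.25 row | ρ = 0.75 row |
|---|---|---|
| Walk | 44.9/89.3 = 0.503: 94.2% | 25.9/89.3 = 0.290: 48.3% |
| Leg | 6.7/13.3 = 0.504: 94.3% | 3.9/13.3 = 0.293: 49.3% |
| Grip | 2.3/4.6 = 0.500: 93.9% | 1.4/4.6 = 0.304: 52.6% |
| Gait | 0.14/0.28 = 0.500: 93.9% | 0.08/0.28 = 0.286: 47.0% |

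**Step 4: if the Table 4 SDs are single-visit SDs.** Table 5's arithmetic then stands, and Table 4 needs the SD of the baseline-to-post change, SD × √(2(1 − ρ)), where ρ is now the baseline-to-post correlation. Two-sample power, 30 per group, two-sided 2.5%:

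| Endpoint | ρ = 0.25 | ρ = 0.50 | ρ = 0.75 |
|---|---|---|---|
| Walk | 105.1/109.37 = 0.961: 91.9% | 98.7% | about 100% |
| Leg | 11.0/16.29 = 0.675: 62.4% | 81.4% | 98.6% |
| Grip | 4.1/5.63 = 0.728: 69.7% | 87.2% | 99.4% |
| Gait | 0.23/0.343 = 0.671: 61.8% | 80.8% | 98.5% |

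**The case against.** The strongest defence is that both tables can be coherent. Section 7.1 uses baseline as a covariate and Section 7.2 names mid-point and final as the time points. Suppose the two repeated values are changes from baseline with equal SDs. Baseline cancels when one is subtracted from the other, so the variance of final minus mid-point is 2 × (SD of change from baseline)² × (1 − ρ), with ρ the correlation between the two change scores. An SD of change is then the right input, all twelve rows are valid and Table 4 stands; the only fault is one symbol used for two quantities. The algebra is correct. But Section 7.5 speaks of mid-point and final measures and assessments and never of change scores, so this reading has to be supplied by the reader.

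Three further points stand:

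- The figures in Step 3 depend on equating the SD of a mid-to-final change with that of a baseline-to-post change. These cover different intervals, and nothing in the documents equates them.
- Treating the values as single-visit SDs contradicts the column symbol and footnote in Table 4. Even then, the effect on power runs in both directions.
- Table 5 concerns a follow-up time effect examined after a significant interaction. Both hypotheses in Section 2.0 compare the supplement with placebo, and Table 5 sets no sample size, test or decision rule.

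A reader might infer that the two tables cannot both be right, that eight of the twelve detectable differences are shown to be wrong, or that 30 per group is shown to be too few. The documents support none of these. The first ignores the change-score reading, the second turns an assumption into a fact, and the third looks only at the low-correlation end of Step 4.

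**Conclusion.** The point holds as an internal inconsistency. As Section 7.5 defines its terms, the derivation and the printed identity are wrong as written, and the same four numbers are used as SDs of change in Table 4 and as single-visit SDs in Table 5. Unless change scores were meant, the tables agree only at ρ = 0.50, a value the documents do not justify.

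The size depends on facts the documents do not give. On the Table 4 label, with the added assumption about the mid-to-final change, the ρ = 0.75 rows carry roughly an even chance of detection and the ρ = 0.25 rows are conservative. On the single-visit reading, the Table 4 powers range from clearly below 80% for leg, grip and gait to well above it. That leaves the support for 30 per group unverified, which is not evidence that it is inadequate.

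These figures keep the plan's own n = 60 for the time effect; whether that is the right number for a within-group test is a separate question. Severity: should be fixed.

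**What to change.** Establish from the pilot data which SD was extracted. In Section 7.5, print the simplification as 2σ²(1 − ρ), define σ and ρ, and use a symbol distinct from Table 4's σ_Δ. Then:

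- **If it is an SD of change:** recompute Table 5 from a mid-to-final change SD, or from single-visit SDs and their correlation. Otherwise state openly that Table 4's SD is assumed to apply and give one detectable difference per endpoint (36.6, 5.5, 1.9 and 0.115). Deleting the ρ rows without that statement would put a baseline-to-post SD on a mid-to-final contrast.
- **If it is a single-visit SD:** keep Table 5, and restate Table 4's label, effect sizes and powers using the pilot baseline-to-post correlation, with a range.
- **If change scores were intended:** say so, and define ρ as the correlation between the two change scores.

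The cost is one look at the pilot data, a corrected formula and a revised table. Sample size and procedures do not change, though some stated powers or detectable differences may become less favourable.
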